4.1.2 Treatment period

Patients will be randomized to receive either BNT111 + cemiplimab combination therapy (Arm 1), BNT111 monotherapy (Arm 2) or cemiplimab monotherapy (Arm 3).

Treatments with BNT111 will be given once-weekly for the first 6 wks, followed by treatments once every 3 wks (±3 d). Cemiplimab will be given once every 3 wks (±3 d) throughout the trial.

The treatment period starts on Day 1 of Cycle 1 and continues for up to 24 months or until confirmed progression of disease, withdrawal of consent or unacceptable toxicity.

4.1.3 Add-on therapy for patients in Arm 2 or 3

Patients who experience disease progression under monotherapy may continue with addon therapy. Disease progression must be verified centrally. The eligibility of patients for the add-on therapy needs to be checked based on the inclusion criteria (Section 5.1.3) and exclusion criteria (Section 5.1.4). Patients need to re-consent for participation in the addon therapy.

Patients in Arm 2 (add-on of cemiplimab to BNT111): Cemiplimab will be given once every 3 wks (±3 d). BNT111 will be continued according to the planned schedule; a patient must have received a total of 6 weekly injections during the initial trial treatment and the add-on therapy before moving to a once every 3 wk schedule of injections.

Patients in Arm 3 (add-on of BNT111 to cemiplimab): BNT111 will be given once-weekly for the first 6 wks of add-on therapy, followed by treatments once every 3 wks (±3 d). Cemiplimab will continue to be given once every 3 wks (±3 d).

Page 45 of 133 Version: 7.0 Date: 09 FEB 2023

Treatments will continue up to a total treatment duration (monotherapy and add-on therapy) of 24 months.

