6.3 Duration of treatments

The duration of treatment with BNT111 + cemiplimab (Arm 1) or BNT111 or cemiplimab as single agents is up to 24 months and will continue until unacceptable toxicity, withdrawal of consent, discontinuation due to investigator's decision or (confirmed) disease progression. Treatment with cemiplimab and/or BNT111 may be continued through initial radiological disease progression if the patient derives clinical benefit, e.g., until symptomatic disease, confirmation of progression, or unacceptable toxicity (whatever comes first).

Patients in Arm 2 (BNT111 monotherapy) or Arm 3 (cemiplimab monotherapy) may enter add-on therapy (addition of the other compound). The start of the add-on therapy should be scheduled with as little therapy interruption as possible and at latest start within 6 wks after confirmed disease progression. The duration of therapy for patients entering into add-on therapy is a total of 24 months for both the monotherapy and add-on therapy part.

If one of the compounds needs to be discontinued, single-agent treatment with the other can continue upon investigator's and sponsor's agreement.

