8.3 Adverse events and serious adverse events

The investigator and any qualified designees are responsible for detecting, documenting, and recording events that meet the definition of an AE or SAE and remain responsible for following up all AEs and SAEs.

8.3.1 Time period and frequency for collecting adverse event and serious adverse event information

All AEs and SAEs will be collected from the first signing of the ICF until the SFU2 visit (90 days after last trial dose or until a new anti-cancer therapy is started) at the time points specified in the SoA (Section 1.3). Additionally, in case a new anti-cancer therapy is started within 90 days after last treatment, the safety follow-up visit should be performed just prior to starting the new anti-cancer therapy. Adverse events after start of new anti-cancer therapy do not need to be reported unless a causal relationship to BNT111-01 or cemiplimab is suspected.

All SAEs (initial and follow-up reports) will be recorded and reported to the sponsor or designee within the appropriate time frame and under no circumstance should this exceed 24 h after knowledge of the event, as indicated in Section 10.3.1.10. AESIs should also be reported within an appropriate time frame (i.e., no more than 24 h after knowledge of the event).

Investigators are not obligated to actively seek AEs or SAEs after a patient has discontinued from the trial. However, if the investigator learns of any SAE, including a death, at any time after a patient has discontinued from the trial, and he/she considers the event to be reasonably related to the trial treatment or trial participation, the investigator must promptly notify the sponsor.

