For add-on of BNT111 to cemiplimab, BNT111 will be given once weekly for the first 6 weeks, followed by treatments once every 3 weeks (±3 d). For add-on of cemiplimab to BNT111, cemiplimab will be given once every 3 weeks (±3 d). Treatments will continue up to a total treatment duration (monotherapy and add-on therapy) of 24 months.

Page 17 of 78 Version: Final v7.0 Date: 05Mar2024

If one of the compounds needs to be discontinued, single agent treatment with the other can continue upon investigator's and sponsor's agreement.

Efficacy is assessed with regular efficacy assessments every 6 weeks for the first 3 months after treatment start, then every 9 weeks for the next 9 months and every 12 weeks thereafter until progressive disease, start of new anti-cancer therapy, withdrawal of consent, death or lost to follow-up.

Safety follow up

The treatment period is followed by a safety follow-up period with visits after 30 and 90 days after last treatment to assess adverse events (AEs). All adverse events will be reported until 90 days after the last dose of trial treatment unless a new anti-cancer therapy is started. If the patient is not able to visit the clinic/hospital, the AE assessment will be done by phone call.

Efficacy follow up

Patients whose last disease assessment on trial treatment was CR, PR or SD will continue to have efficacy assessments.

Survival follow up

Patients will be followed for survival every 3 months for approximately up to 48 months of OS follow-up from the randomization of the last patient.

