8 STATISTICAL ANALYSES

8.1 General considerations

In general, the statistical analysis of efficacy will be performed by treatment group. Exploratory analysis will be performed for patients in the calibrator arms who went on to receive add-on treatment.

No formal statistical comparisons between treatment groups will be performed.

Continuous variables will be summarized by treatment group and total (as specified) using the following descriptive statistics: number of patients with non-missing data (n), mean, standard deviation (SD), median, minimum (min) and maximum (max).

Categorical variables will be summarized by treatment group and total (as specified), presenting absolute and relative frequencies (n and %) of patients in each category and the number of patients with missing data (missing' category will be presented if there is one or more missing value). The "(N=xx)" in the tables denotes the number of patients in the

Statistical Analysis Plan (SAP) BNT111-01

Page 28 of 78 Version: Final v7.0 Date: 05Mar2024

analysis set within each treatment group. For event-driven occurrence data (e.g., adverse event, concomitant medication, etc.) the percentages will be based on the number of patients in the analysis set (N). For reported visit data (e.g., gender, ECOG, etc.) the percentages will be based on the number of patients with non-missing values (n).

The rates of binary endpoints will be summarized by treatment group with absolute and relative frequencies (n and %) along with two-sided 95%-confidence intervals (CI) using an exact method. Exact confidence intervals for binomial proportions will be derived using the Clopper-Pearson method (Clopper, CJ and Pearson, ES⁵).

Time-to-event-endpoints will be analyzed using Kaplan-Meier methodology by treatment group and censored in accordance with the FDA Guidance: "Clinical Trial Endpoints for the Approval of Non-Cell Lung Cancer Drugs and Biologics² (Table 5.1). The main analysis will be done for each treatment group separately. Comparison of the treatment groups may be done as an exploratory analysis, with stratified and non-stratified analysis considered.

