8.5.2 Adverse events

Adverse events (AEs) will be coded using Medical Dictionary for Regulatory Activities (MedDRA®) coding system version 23.1 or later to get a System Organ Class (SOC) and Preferred Term (PT) for each AE and graded for severity using NCI CTCAE v5.0. In case a patient has an AE with missing relationship status, the event will be assumed to be related and associated with the treatment received in the summaries (will be listed as collected in the listings). No imputation for missing NCI-CTC grades will be performed.

TEAEs for randomized treatment

A treatment-emergent AE (TEAE) is defined as any AE with an onset date on or after the first administration of trial treatment (if the AE was absent before the first administration of

Statistical Analysis Plan (SAP) BNT111-01

Page 46 of 78 Version: Final v7.0 Date: 05Mar2024

trial treatment) or worsened after the first administration of trial treatment (if the AE was present before the first administration of trial treatment). AEs with an onset date more than 90 days after the last administration of trial treatment will be considered as treatment emergent only if assessed as related to trial treatment by the investigator, prior to start of Add-on treatment, if applicable, whichever comes first.

An AE will be considered TE for the randomized treatment if it started within 90 days of last dose of randomized treatment or until start of add-on treatment whichever comes first.

Add-on TEAEs

Treatment-emergent for add-on treatment is defined as any AE with an onset date on or after the first administration of add-on treatment (if the AE was absent before the first administration of add-on treatment) or worsened after the first administration of the add-on treatment (if the AE was present before the first administration of add-on treatment). AEs with an onset date more than 90 days after the last administration of add-on treatment will be considered as TE only if assessed as related to add-on treatment by the investigator.

TEAEs for both randomized and add-on treatment

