The number and percentage of patients reporting TEAEs will be summarized by PT nested within SOC. If a SOC / PT is reported more than once for a patient, the patient will only be counted once for this SOC / PT. Strongest relationship or worst grade will be counted if a TEAE is reported more than once by the same patient for a SOC / PT.

All AE summary tables will be presented for BNT111 and cemiplimab separately and sorted alphabetically by SOC and PT within SOC.

Analyses of other adverse events (excluding serious AEs)

The number and percentage of patients reporting other TEAEs (excluding TESAEs) will be summarized by PT nested within SOC. If a SOC / PT is reported more than once for a patient, the patient will only be counted once for this SOC / PT.

All AE summary tables will be presented for BNT111 and cemiplimab separately and sorted alphabetically by SOC and PT within SOC.

Treatment-related AEs

The number and percentage of patients reporting treatment-related TEAEs will be summarized by PT nested within SOC for BNT111 and cemiplimab separately and related to both the treatments.

Statistical Analysis Plan (SAP) BNT111-01

Page 48 of 78 Version: Final v7.0 Date: 05Mar2024

In addition, treatment-related for both randomized and add-on treatment TEAEs will be summarized by PT nested within SOC for BNT111 and cemiplimab separately.

AESIs (irAE and Infusion-related AEs)

The number and percentage of patients with AESIs, irAEs grade ≥3 related to cemiplimab and infusion-related reactions grade ≥2 related to cemiplimab will be summarized by PT nested within SOC.

TEAE by NCI-CTCAE grade

The number and percentage of patients with TEAEs will be summarized by worst NCI-CTCAE grade by PT nested within SOC. Worst grade will be counted if a TEAE is reported more than once by the same patient for a SOC / PT.

TEAE by NCI-CTCAE grade by relationship status

The number and percentage of patients with related and not related TEAEs will be summarized by worst NCI-CTCAE grade by PT nested within SOC for BNT111 and cemiplimab separately. Worst grade will be counted if a TEAE is reported more than once by the same patient for a SOC / PT.

Serious Adverse Events

The number and percentage of patients with TESAEs will be summarized by PT nested within SOC.

Related Serious Adverse Events

The number and percentage of patients with related TESAEs (for BNT111 and cemiplimab separately and related to both the treatments) will be summarized by PT nested within SOC.

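### AE tables give crude percentages over observation windows that can differ by arm; add exposure-adjusted rates and one common-window table

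*SAP*

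**What the plan says.** SAP 8.5.2 defines the randomized-period window: an AE belongs to the randomized treatment "if it started within 90 days of last dose of randomized treatment or until start of add-on treatment whichever comes first". Add-on exists only for Arms 2 and 3 (SAP 3.2; Protocol 4.1.3).

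The display is a count and a percentage: "The number and percentage of patients reporting TEAEs will be summarized by PT nested within SOC". For event-type data such as AEs, SAP 8.1 fixes the denominator: "the percentages will be based on the number of patients in the analysis set (N"), that is, patients and not time.

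A second stop applies in every arm. SAP 3.2: "All adverse events will be reported until 90 days after the last dose of trial treatment unless a new anti-cancer therapy is started". Protocol 8.3.1 adds the exception for related events: "Adverse events after start of new anti-cancer therapy do not need to be reported unless a causal relationship to BNT111-01 or cemiplimab is suspected".

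Treatment limits are the same in all arms. The treatment period "continues for up to 24 months or until confirmed progression of disease, withdrawal of consent or unacceptable toxicity" (Protocol 4.1.2). Add-on is to begin with little interruption and "at latest start within 6 wks after confirmed disease progression" (Protocol 6.3).

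SAP 8.5.2 also plans add-on TEAE tables and combined randomized-plus-add-on tables, and SAP 8.5.1 tabulates exposure. Neither document plans an exposure-adjusted AE rate, a time-to-first-AE analysis or an AE table over a window common to all arms.

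**The concern.** The secondary safety objective covers Arm 1 and each single agent, and the calibrator arms exist to show what each component contributes. Readers will set the three columns side by side. A crude percentage rises with observation time even when the event rate does not.

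Two things can make that time unequal. The add-on cut removes part of the post-treatment tail for monotherapy patients who cross over. Time on treatment may also differ, since treatment stops at confirmed progression. A gap between columns then mixes toxicity with follow-up. The rows most exposed are those with late events: immune-related AEs, which Protocol 8.4 says may appear several months after the last dose, and deaths from progression within 90 days, which Protocol 8.3.6 counts as Grade 5 SAEs.

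**Working it through.** The documents give no AE rate, add-on uptake or expected treatment time, so there is no figure of the plan's own to reproduce. The check asks how far the crude percentages can part when the true event rate is the same in every arm.

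**Inputs from the documents**
- Tail after last dose: 90 days, which is 90/30.4375 = 2.957 months (SAP 8.5.2; month length from SAP 8.1).
- Treatment cap: 24 months in every arm.
- Add-on start: 0 to 42 days after confirmed progression.

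**Assumptions**
- Time on treatment T is exponential with median 3 months, rate μ = ln 2/3 = 0.2310 per month, and treatment ends at progression.
- First-event hazard λ = 0.10 per month in every arm.
- Add-on starts 21 days (0.690 months) after treatment ends, in 50% or 70% of monotherapy patients.

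**Formula.** Crude incidence = 1 − E[exp(−λW)], where W = min(T, 24) + tail. The treatment part is

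E[exp(−λ·min(T, 24))] = μ/(μ+λ) + [λ/(μ+λ)]·exp(−24(μ+λ)) = 0.698.

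**1. Add-on cut alone (equal treatment time, full 90-day Arm 1 tail)**
- Arm 1, and monotherapy patients without add-on: 1 − 0.698 × exp(−0.2957) = 1 − 0.698 × 0.744 = 48.1%.
- Monotherapy patients entering add-on: 1 − 0.698 × exp(−0.0690) = 1 − 0.698 × 0.933 = 34.8%.
- 50% uptake: 0.5 × 34.8 + 0.5 × 48.1 = 41.5%, a gap of 6.6 points.
- 70% uptake: 0.7 × 34.8 + 0.3 × 48.1 = 38.8%, a gap of 9.3 points. Mean windows are 7.3 v 5.7 months.

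Across medians of 3 and 6 months, uptake of 40 and 70%, add-on gaps of 0 to 42 days and hazards of 0.02 to 0.30 per month, the gap with a full 90-day Arm 1 tail runs from 1.0 to 17.9 points.

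**2. New therapy shortens the Arm 1 tail**
- Arm 1 tail 42 days, add-on at 42 days: 39.2% v 39.2%, no gap.
- Arm 1 tail 28 days, add-on at 42 days, 70% uptake: 36.3% v 38.3%, a reversal of 2.0 points. Over the grid the reversal is 0.3 to 3.0 points.
- Half of Arm 1 starting new therapy at 0.75 months and half of monotherapy starting add-on at 0.75 months: the windows have the same distribution, so both arms are at about 42%.

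**3. Arm 1 treated longer (median 6 v 3 months, 70% uptake, 21-day gap, 90-day tail)**
- The treatment part for a 6-month median is 0.539, so Arm 1 = 1 − 0.539 × 0.744 = 59.9%.
- Monotherapy is 38.8%, a gap of 21.1 points. Without the add-on cut, monotherapy would be 48.1%, so 11.9 of the 21.1 points come from time on treatment alone.

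**4. Does a person-time rate remove the artefact?**
- Simulated first events per 100 patient-months in case 1 at 70% uptake: 10.0 v 10.1, true value 10. In case 3: 10.0 v 10.0.
- The definition of time at risk matters. With half of Arm 1 on new therapy at 0.75 months and no later events captured, letting time run on to 90 days returns about 8.5 instead of 10. Ending it at new therapy restores 9.9 to 10.0.

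**The case against.** The strongest counter-argument is the new-therapy stop. A reader might infer from SAP 8.5.2 alone that Arm 1 always keeps its full treatment period plus 90 days, and so must look more toxic. The documents do not support that. Collection of AEs not suspected to be related ends at new anti-cancer therapy in every arm, and an Arm 1 patient who progresses may go on to one. Working step 2 shows the gap can then vanish or reverse. This stands, and it is why the direction is only likely. It is not a full answer: suspected-related AEs remain reportable after new therapy, and Protocol 8.3.6 states no new-therapy exemption for deaths within 90 days.

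Second, a reader might charge the whole gap in a scenario such as 59.9% v 38.8% to the add-on rule. More than half of it comes from an assumed longer Arm 1 treatment, for which the documents give no estimate.

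Third, a constant hazard fits much BNT111 toxicity poorly. Protocol 2.3.1 places hypotension within hours of dosing, typically at the first or second vaccination. Add-on requires prior progression, so such events mostly fall before the cut. This also stands.

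Fourth, SAP 8.1 says "No formal statistical comparisons between treatment groups will be performed", and exposure is tabulated. True, but exposure tables are not AE time at risk and are not linked to AE counts. The combined table mixes combination exposure into the monotherapy columns. The cut itself is reasonable, because after add-on the patient receives both drugs; what is missing is a denominator that respects it.

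**Conclusion.** The point holds in a limited form. The AE tables use crude percentages over windows that can differ by arm, and nothing planned adjusts for this. With equal event rates Arm 1 can look more toxic: about 48% v 39 to 42% from the add-on cut alone, under the hazard, treatment time, uptake and full 90-day tail assumed above. None of those inputs except the 90 days is in the documents. The gap is zero or slightly negative if new therapy cuts the Arm 1 tail to the add-on gap or less, and larger if Arm 1 is treated longer. A certain bias against the combination is not established. The matter affects descriptive safety tables only, and is a cheap improvement.

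**What to change.** In SAP 8.5.2, for the TEAE, Grade ≥3, serious and irAE rows of the randomized period, show beside the crude percentage the exposure-adjusted incidence: patients with a first event per 100 patient-months at risk.

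- Time at risk ends at the earliest of first event, 90 days after last dose, the day before add-on, start of new anti-cancer therapy, death, loss to follow-up or data cut-off.
- Count only events that fall inside that time at risk.
- For rows restricted to related AEs, which stay reportable after new therapy, do not end time at risk at new therapy.
- Add one AE table limited to the first two cycles, with a note that Arm 3 has no C1D8, C1D15, C2D8 or C2D15 visits, so AEs are asked about less often there.

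The cost is a few added columns and one table, with no new data collection. The rate assumes a roughly constant hazard, a limitation that the two-cycle table partly offsets.
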